1. INTRODUCTION

1.1 Background

Multiple Sclerosis

Multiple Sclerosis (MS) is chronic inflammatory disease affecting the central nervous system (CNS). MS is the most common cause of non-traumatic neurological disability among young adults in the Western Hemisphere. It affects over 400,000 individuals in the United States alone, approximately 2.5 million people worldwide, and its incidence is on the rise. The symptoms of MS are protean, reflecting the multifocal nature of the disease. They include visual loss, spastic paraparesis, numbness, urinary incontinence, gait imbalance, fatigue, double vision, tremor and cognitive impairment.

In the majority of cases, MS initially follows a relapsing-remitting (RRMS) course characterized by discrete episodes of neurological symptoms separated by clinically quiescent periods. Peripheral blood leukocytes cross the blood-brain-barrier (BBB) and infiltrate the brain, spinal cord and optic nerves to drive parenchymal lesion formation. Clinical exacerbation correlates with the development of lesions in “eloquent” areas. Natural history studies have shown that the incidence of relapses and breaches in the BBB decrease with disease duration (Filippi et al., 1997). However, the majority of individuals with RRMS ultimately enter a secondary progressive (SP) stage, characterized by the gradual accumulation of neurological disability. The molecular and cellular basis for this transition is unclear, and the role of inflammation during the SP stage is a subject of active debate. In fact, immunomodulatory disease modifying agents (DMA) that are used to manage RRMS tend to lose efficacy following transition to a SPMS stage (Panitch et al., 2004, Paolillo et al., 1999). Such observations have led to the proposal that the gradual accumulation of disability in SPMS is driven by neurodegeneration, manifested as neuronal cell death, Wallerian degeneration and astrogliosis, independent of the autoimmune assault that predominates earlier in the disease course (Trapp and Nave, 2008).

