4.2 Exclusion Criteria

1. Absolute medical contraindication to corticosteroid treatment
2. Absolute medical contraindication to receive ECP
3. Clinical relapse within 2 years of screening
4. Laboratory evidence of any of the following:
 - a. WBC $< 2,000$ cells per uL
 - b. Serum transaminase levels $> x 2$ UNL
 - c. Creatinine Clearance < 60 mL/min
 - d. HgbA1C $> 6\%$

5. Concurrent diagnosis of a neurological condition that would interfere with the assessment of MS, or an autoimmune disease or inflammatory condition that is chronically treated with immunosuppressive agents, including systemic corticosteroids.
6. Evidence of known infection with human immunodeficiency virus (HIV) or active (not including latent) Hepatitis B (laboratory testing is not required if virus status is already known)
7. Uncontrolled infection requiring treatment at study entry
8. Hypersensitivity or allergy to psoralen (methoxalen)
9. Hypersensitivity or allergy to both heparin and citrate products (If hypersensitive or allergic to only one of these products, exclusion does not apply)
10. Inability to tolerate fluid changes associated with ECP (e.g. inadequate renal, hepatic, pulmonary and cardiac function leading to enable patient to tolerate extracorporeal volume shifts associated with ECP)
11. Presence of aphakia or photosensitive disease (systemic lupus erythematosus, porphyrias, albinism, etc.)
12. Women who are pregnant and/or lactating.
13. Use of any investigational drug/treatment at the time of enrollment or within the previous 60 days, or five elimination half-lives, or until the expected pharmacodynamic effect has returned to baseline, whichever is longer.
14. Initiation of dalfampridine or change in the dose of dalfampridine within 6 months prior to randomization
15. Treatment with any of the medications or procedures listed below:
 - Glatiramer acetate, interferon-beta, fingolimod, teriflunomide or dimethylfumarate within 3 months prior to randomization
 - Natalizumab within 3 months prior to randomization
 - Cyclophosphamide within 1 year prior to randomization
 - Mitoxantrone within 1 years prior to randomization
 - Rituximab within 6 months prior to randomization
 - Ofatumumab, ocrelizumab, cladribine, daclizumab within 2 years prior to randomization
 - Intravenous immunoglobulin within 6 months prior to randomization
 - Plasmapheresis within 6 months prior to randomization

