5. PATIENT WITHDRAWAL AND REPLACEMENT

Patients may withdraw from the study at any time without penalty and for any reason without prejudice to his or her future medical care.

Patients must be withdrawn under the following circumstances:

- The patient withdraws consent
- Pregnancy (see Section 8.2.2.9)
- Unacceptable toxicity including patients on corticosteroids who develop psychosis or aseptic necrosis of the femoral head

Patients may be required to withdraw after discussion with the investigator for the following reasons:

- AE(s)
- At the discretion of the investigator
- Violation of eligibility criteria
- Deviation from the treatment plan specified in the protocol (e.g., incorrect administration of the study drug, failure to attend study visits, etc.)
- The treating physician can withdraw the patient from the study at any time and for any medical reason that he/she deems necessary
- The patient has a right to withdraw at any time, for any medical or other reasons.
- Patients who experience a clinical relapse (defined as neurological event characterized by new or worsening symptoms lasting 48 hours after a stable period of at least 30 days and is considered in the judgment of the investigator to be a clinical relapse). Patients who fail therapy will be off study, and further therapy will be at the discretion of the treating neurologist. The study will not cover any form of therapy after the patient is off study.
- Patients who have interval accumulation of T1 or T2 lesions and/ or gadolinium enhancing T1 lesions on the month 6 MRI scan
- In all cases, the reason(s) for withdrawal, and the primary reason, must be recorded on the case report form (CRF) or similar.

Withdrawn patients will be replaced.

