7.5 Concomitant Medications

Any medication the patient takes other than the study drug, including herbal and other non-traditional remedies during the 52 Week study, is considered a concomitant medication. All concomitant medications must be recorded in the CRF. The following information must be

recorded in the CRF for each concomitant medication: generic name, route of administration, start date, stop date, dosage, and indication. Any changes in the dosage or regimen of a concomitant medication must be recorded in the CRF.

At Screening, patients will be asked what medications they have taken during the last 30 days and what concomitant medication they are taken. At each subsequent study visit, patients will be asked what concomitant medications they are currently taking.

The following drugs/therapies are permitted at the investigator's discretion:

- Medications to prevent infection (pneumocystis, viruses and fungal organisms, etc.) per institutional practice.
- Venous access for ECP (at investigator's discretion and per institutional practice).
- Systemic steroids may be administered for clinical relapse or the emergence of gadolinium enhancing MRI lesions.

The following drugs/therapies are prohibited during the treatment period of the study:

- Tysabri® (natalizumab) or other intravenous DMA
- Initiation of dalfampridine or change in the dose of dalfampridine within 6 months prior to randomization
- Treatment with any of the medications or procedures listed below:
- Glatiramer acetate, interferon-beta, fingolimod, teriflunomide or dimethylfumarate within 3 months prior to randomization
- Natalizumab within 3 months prior to randomization
- Cyclophosphamide within 1 year prior to randomization
- Mitoxantrone within 1 years prior to randomization
- Rituximab within 6 months prior to randomization,
- Ofatumumab, ocrelizumab, cladribine, daclizumab within 2 years prior to randomization
- Intravenous immunoglobulin within 6 months prior to randomization
- Plasmapheresis within 1 year prior to randomization

Corticosteroids within 3 months prior to screening, with the following exceptions: Topical ointments or creams, or eye drops that contain corticosteroids; Intranasal Steroids or Oral Steroids given in a single dose as a premedication for a procedure such as gadolinium-enhanced MRI.

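### Section 7.5 is headed as an on-study prohibition, but after its first bullet every item carries only a pre-entry window, so an on-study dalfampridine start or dose change is not barred as written

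*Combined protocol and SAP*

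**What the plan says.** The list in Section 7.5 opens with "The following drugs/therapies are prohibited during the treatment period of the study". Its first bullet, ending "natalizumab) or other intravenous DMA", has no time limit and can operate during treatment. The next is "Initiation of dalfampridine or change in the dose of dalfampridine within 6 months prior to randomization", the same text as exclusion 14 in Section 4.2. The drug and procedure items that follow repeat exclusion 15, and the closing corticosteroid sentence repeats exclusion 16; all look back from randomisation or screening. One item was altered in the copying: 7.5 has "Plasmapheresis within 1 year prior to randomization" and 4.2 has "Plasmapheresis within 6 months prior to randomization".

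Other relevant text:

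- Section 7.5 permits some steroid use: "Systemic steroids may be administered for clinical relapse or the emergence of gadolinium enhancing MRI lesions". It also requires every concomitant medication, with dates and dose changes, to be entered in the CRF.
- Section 5 says "Patients who fail therapy will be off study, and further therapy will be at the discretion of the treating neurologist". It also lets the investigator withdraw a patient for departing from the treatment plan.
- Section 10.2.1 counts patients who withdraw as non-responders. It makes a 20% rise in the timed 25-foot walk sufficient on its own for progression.
- Section 9.1 lets the Week 52 visit fall up to 1 month either side.

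**The concern.** A window that closes at randomisation cannot restrict anything afterwards. Read literally, a dalfampridine start at month 8 breaks no stated rule, and a monitor checking adherence would have nothing to hold it against.

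The plan itself treats such a change in the 6 months before randomisation as disqualifying, so it evidently does not want one near a measurement of disability. Walking enters the primary endpoint twice: through the timed walk, and through the EDSS, which Section 8.1.2 describes as driven largely by ambulation in its middle range. The trial is open-label, so starts could differ by arm. Any effect on walking would then be credited to the randomised treatment, or would mask it.

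A bar tied strictly to the treatment period could also lapse before a late Week 52 assessment.

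**Working it through.** **Text check.** Each item in 7.5 against its source in 4.2:

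| Item in 7.5 | Time limit in 7.5 | Source in 4.2 | Operates on study? |
|---|---|---|---|
| Natalizumab, other intravenous agents | none | – | yes |
| Dalfampridine start or dose change | 6 months before randomisation | exclusion 14, identical | no |
| Oral and injectable agents | 3 months before randomisation | exclusion 15, same | no |
| Plasmapheresis | 1 year before randomisation | exclusion 15, 6 months | no |
| Corticosteroids | 3 months before screening | exclusion 16, same | no |

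The remaining exclusion 15 items follow the same pattern, though those that count as intravenous disease-modifying agents stay barred by the first bullet. One further bullet has no window, but it only introduces the sub-list. No other section bars these starts after randomisation.

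**The plan's power figure.** Inputs from Section 10.4: 30% v 60% without progression, 33 per arm, one-sided 5%. With the pooled-variance normal approximation and mean rate 0.45:

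Power = Φ{[0.30 − 1.645 × √(2 × 0.45 × 0.55/33)] / √[(0.30 × 0.70 + 0.60 × 0.40)/33]} = Φ{[0.30 − 1.645 × 0.1225]/0.1168} = Φ(0.844) = 80.1%.

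This agrees with the stated value of at least 80%.

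**Illustration.** The same pooled z-test (reject if z > 1.645) was evaluated by exact enumeration of both binomials. Base case: rejection 5.2% at 30% v 30%, and power 81.2% at 30% v 60%.

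Assumed, not in the documents: *k* patients in an arm start dalfampridine and a fraction *f* of their progressions is averted. The arm's non-progression rate becomes p + (k/33) × (1 − p) × f.

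- k = 2, f = 0.25: 0.30 + (2/33) × 0.70 × 0.25 = 31.1%; and 0.60 + (2/33) × 0.40 × 0.25 = 60.6%.
- k = 4, f = 0.50: 0.30 + (4/33) × 0.70 × 0.50 = 34.2%; and 0.60 + (4/33) × 0.40 × 0.50 = 62.4%.

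| Where the starts fall | Quantity | k = 2, f = 25% | k = 4, f = 50% |
|---|---|---|---|
| ECP only, no treatment effect | false positives | 6.2% | 10.2% |
| Control only, ECP at 60% | power | 78.6% | 69.8% |
| Same number in both arms | false positives | 5.1% | 5.0% |
| Same number in both arms | power | 80.1% | 76.6% |

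With no starts, or no effect of a start, the base case applies.

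**The case against.** The strongest reply is that this is a paste error with an obvious meaning. A pre-randomisation event cannot be prohibited during treatment, so a sensible site would read the list as an on-study bar. The plan also has backstops: starts and dose changes must be recorded and so would be visible by arm, and an investigator who regards a start as a deviation may withdraw the patient, who then counts as a non-responder.

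Most of this stands, and it lowers the weight of the point. It does not close the gap. Recording is not a bar. Withdrawal for deviation is discretionary, its examples do not mention concomitant drugs, and it presupposes a rule to deviate from. Two readers could classify the same dalfampridine start differently.

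It is also fair that the documents nowhere say dalfampridine improves walking, or that patients would start it. The counts, the effect and the one-arm imbalance in the illustration are assumptions, and the balanced case shows little harm.

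Two stronger readings are tempting:

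- *That the plan deliberately leaves these therapies open.* The heading of the list contradicts this.
- *That the primary result would be biased, or biased towards ECP.* No uptake, imbalance or effect is given, so neither size nor direction can be claimed.

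Nor is the risk equal across the list. Section 1.1 says disease-modifying agents "tend to lose efficacy following transition to a SPMS stage", and the off-study rule for patients who fail therapy narrows the gap for those agents and for plasmapheresis.

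**Conclusion.** The drafting fault is certain: apart from the first bullet, the prohibition in 7.5 cannot operate on study, and its plasmapheresis window disagrees with 4.2. What remains exposed after Section 5 and CRF recording is chiefly a dalfampridine start or dose change in a patient who stays on study.

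The consequence is uncertain. Under the assumed one-arm starts, false positives would be about 6–10% against 5.2%, or power 79–70% against 81%. Under balanced starts the figures are about 5% and 80–77%. These show only that with 33 per arm a few unequal starts could matter; they do not forecast that they will.

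This takes Week 52 as the primary time point, as Sections 3.2.1 and 10.2.1 state, although the Synopsis endpoint entry says 2 years. The late-visit point is marginal: at most about one month, and the visit may equally fall early. The correction is worth making because it costs almost nothing.

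**What to change.** In Section 7.5, keep every named drug and procedure but delete the pre-entry windows, leaving those only in 4.2. This also removes the plasmapheresis conflict. Then state:

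- From randomisation to the Week 52 assessment, and while the patient remains on study, dalfampridine is not to be started or its dose changed.
- Over the same period there is to be no use of natalizumab or any other intravenous disease-modifying agent; interferon-beta, glatiramer acetate, dimethylfumarate, fingolimod or teriflunomide; cyclophosphamide, mitoxantrone or rituximab; cladribine, daclizumab, ocrelizumab or ofatumumab; intravenous immunoglobulin; or plasmapheresis.
- Systemic steroids are allowed only as assigned or as 7.5 already permits, keeping the existing topical, intranasal and single-dose premedication exceptions.
- Patients who go off study are treated as Section 5 says.

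The intent-to-treat primary analysis and the sample size do not change. The cost is a wording amendment and at most about one extra month of restriction, when the Week 52 visit falls late. The bar would not cover the second-year EDSS and MSFC assessments, which are secondary.

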8. PARAMETERS AND METHODS OF ASSESSMENT

8.1 Efficacy Parameters

8.1.1 MSFC

The MSFC components can be found in Appendix 1. This scoring system should be administered after reading the manual to ensure that a standardized format should be followed. The MSFC consists of the following components and should be done in the following order:

1. Trial 1: Timed 25-Foot Walk
2. Trial 2: Timed 25 Foot Walk
3. Trial 1: Dominant Hand, 9-HPT
4. Trial 2: Dominant Hand, 9-HPT
5. Trial 1: Non-Dominant Hand, 9-HPT
6. Trial 2: Non-Dominant Hand, 9-HPT
7. PASAT-3”

An individual component should be discontinued only if the patient meets the discontinue criteria for that component. Other components should still be administered.

Every effort should be made to use the same testing room and the same designated area for the Timed 25 Foot Walk at every visit. It is essential that that the potential for external distraction be kept to a minimum. If the space designated for the Timed 25 Foot Walk is in a public hallway, complete privacy may be impossible, however, every attempt must be made to keep the patient’s path clear of obstacles (human and inanimate). No one other than the examiner and the patient should be in the testing room during 9-HPT and PASAT. The first time a subject takes the PASAT, practice sequences are initially administered a maximum of 3 times.

The response definitions are as below:

An MSFC score is created from the tests done above. Details can be found in the publication referenced (Fischer et al). The composite consists of Z score from the components tested and compared using normals to standardize the scored. The MSFCS is a continuous variable that can be used as any numerical variable in analyses. The value is subject to tests appropriate for continuous variables, such as t-tests, Analysis of variance and regression analysis as well as nonparametric test. A composite based on such Z-scores can also measure change in performance over time. By computing the composite at one point in time and measuring the patient at a later point in time, the arithmetic difference between MSFC scores can be used to measure improvement or worsening.

8.1.2 EDSS

The EDSS form can be found in Appendix 2. The scores are calculated from the Functional System Score (FSS). EDSS and FSS will be determined by a single neurologist at baseline, and every 3 months through 2 years.

The EDSS is an ordinal scale with a 0.5-point increments ranging from 0-10.0. (increasing score indicates worsening) and based largely on ambulatory impairment in its middle range (EDSS 4.5-7.5 points).

0= normal neurological exam

10=death due to MS

Score 6 is still ambulatory with assistance

Score of 7 means patient must use a wheelchair.

8.1.3 MRI

All patients will be evaluated with cranial MRI examination on a 1.5 tesla strength magnet at baseline and months 6 and 12 using the following sequences: axial T2-weighted, axial and sagittal T1 weighted, axial and sagittal fluid attenuated inversion recovery (FLAIR), post Gadolinium axial and coronal T1 weighted images. The total number of gadolinium enhancing T1-weighted lesions and interval changes in the number and size of T-weighted, FLAIR and T1-weighted lesions will be determined by a board certified neuro-radiologist.

8.2 Safety Parameters

8.2.1 Immunological Studies

The following immune parameters will be measured at baseline, and again at 3, 6, 9 and 12 months. Frequency of myelin basic protein-specific IFN γ or IL-17 producing PBMC, Frequency of tetanus toxoid –specific IFN γ or IL-17 producing PBMC, plasma levels of IFN γ , IL-17, IL-4, IL-10, IL-12, IL-21, IL-23, CCL2, GRO α , CXCL8, CXCL10, CCL11, CXCL13, GM-CSF, G-CSF and neutrophil elastase. Additional inflammatory molecules might be measured based on preliminary findings.

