10.2.2 Analysis of Secondary Endpoints

The secondary endpoints include:

- Change in Plasma levels of Immunological Factors and Frequencies of IFN γ and IL-17 MBP-specific PBMC at months 3, 6, 9 and 12 compared with baseline
- MSFC 3 dimensional composite z-score at every 3 month time point through 2 years compared to baseline
- Expanded Disability Status Scale (EDSS) score at every 3 month time point through 2 years compared to baseline
- Percentage of subjects with improvement (as defined for the primary endpoint) at months 3, 6, 9 and 12 compared to baseline
- Occurrence of clinical relapse at any point in the study

- Interval change in T2 lesion number and volume on MRI scans obtained at months 6 and 12 compared to baseline
- The number and volume of gadolinium enhancing lesions on MRI scans obtained at months 6 and 12 compared to baseline
- Interval change in the number and volume of gadolinium enhancing lesions on MRI scans obtained at months 6 and 12 compared to baseline.
- Toxicity and Adverse events in both arms

For continuous outcomes, two-sample t-tests or Wilcoxon rank sum tests will be used to compare the treatment arms. For categorical outcomes, Chi-square tests or Fisher's exact test will be used to compare the treatment arms. The proportion of subjects who experience adverse events and serious adverse events will be summarized by treatment group descriptively; no inferential tests will be performed.

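### The first secondary endpoint implies about 72 separate immune-marker tests with no error control, so 3.6 chance findings are expected at 5% per test if the arms do not differ

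*Combined protocol and SAP*

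**What the plan says.** Section 8.2.1 sets the measurements and their timing: "The following immune parameters will be measured at baseline, and again at 3, 6, 9 and 12 months". The list has three parts:

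- two MBP-specific frequencies, IFN-gamma and IL-17 ("Frequency of myelin basic protein-specific IFN" begins that item);
- two tetanus-toxoid frequencies ("Frequency of tetanus toxoid" begins that item);
- plasma IFN-gamma, followed by "IL-17, IL-4, IL-10, IL-12, IL-21, IL-23, CCL2, GRO"-alpha and "CXCL8, CXCL10, CCL11, CXCL13, GM-CSF, G-CSF and neutrophil elastase".

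The list is left open: "Additional inflammatory molecules might be measured based on preliminary findings".

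In sections 3.2.2 and 10.2.2 the first secondary endpoint is change in plasma immunological factors together with IFN-gamma and IL-17 "MBP-specific PBMC at months 3, 6, 9 and 12 compared with baseline". Tetanus-toxoid responses are not named there.

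The only method given is general: "For continuous outcomes, two-sample t-tests or Wilcoxon rank sum tests will be used to compare the treatment arms". Section 10.2.2 withholds inferential testing for adverse events alone. Section 10 gives no significance level for secondary tests, no adjustment, no key marker or visit, no baseline-adjusted or repeated-measures model, and no exploratory label for the immune data. A one-sided 5% error appears in section 10.4, for the primary sample size only.

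**The concern.** A large family of tests without error control produces some nominally significant results even when the treatments do not differ. The plan gives no way to tell those from real effects. Section 2.2 makes the immune effects the first secondary objective and relating immune changes to clinical outcome the second, so chance findings could be carried forward into the interpretation of the clinical results.

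Four visits on one marker are also repeated measures on the same patient. Testing each visit separately ignores that correlation and multiplies the number of tests.

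Finally, the list can grow, and the plan gives no selection rule and no separate place to report the additions.

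**Working it through.** **The plan's own figure.** The plan gives no error or power figure for the immune tests. Its only one is in section 10.4: 33 per arm, 30% versus 60%, one-sided 5%, at least 80% power. With pooled proportion 0.45:

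- numerator: 0.30 x sqrt(33) - 1.645 x sqrt(2 x 0.45 x 0.55) = 1.723 - 1.157 = 0.566
- denominator: sqrt(0.30 x 0.70 + 0.60 x 0.40) = 0.671
- z = 0.844, so power = 80.06%

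That figure reproduces. It says nothing about secondary tests, so 5% per test is an assumption below and a range is shown.

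**Counting markers (section 8.2.1, matched to the endpoint in 10.2.2).**

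- Plasma: IFN-gamma plus 8 in the first part of the list = 9, plus 7 in the rest = 16
- MBP-specific frequencies: 2
- In the endpoint: 16 + 2 = 18
- Measured but not named in the endpoint: 2 tetanus-toxoid frequencies (18 + 2 = 20 measured in all)

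**Counting tests.** Four post-baseline visits, one between-arm test per marker and visit: 18 x 4 = 72.

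**Expected false positives if the arms differ on no marker** (tests x level):

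| Level per test | 72 tests |
|---|---|
| 2.5% | 1.8 |
| 5% | 3.6 |
| 10% | 7.2 |

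Each added marker contributes 4 x 0.05 = 0.2 more.

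**Chance of at least one, if independent:** 1 - 0.95^72 = 97.5%.

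**Effect of correlation.** The expected count does not depend on correlation, but the chance of at least one does. A simulation with 33 per arm used all 20 measured parameters (80 t-tests at 5%, expected 80 x 0.05 = 4.0), a slightly larger set than the endpoint. The correlations are assumed.

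| Correlation between markers / visits | Mean count | At least one | 5th to 95th percentile |
|---|---|---|---|
| 0 / 0 | 4.0 | 98% | 1 to 7 |
| 0.3 / 0.5 | 4.1 | 93% | 0 to 11 |
| 0.5 / 0.7 | 4.1 | 77% | 0 to 15 |

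Correlated false positives cluster, so a single trial may show none or many.

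**One test per marker instead:** 18 tests, 18 x 0.05 = 0.9 expected.

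**The case against.** The strongest reply is that this is a 66-patient, single-centre Phase II study with one primary endpoint. No decision, sample size or success claim rests on an immune p-value, and broad marker screening is reasonable at this stage. That stands, and it limits the weight of the point. It does not remove it, because the plan lists these comparisons as an inferential secondary endpoint and not as descriptive or exploratory work.

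A reader might also infer more than the documents support:

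- **Twenty markers, 80 tests and four expected false positives.** This counts the tetanus-toxoid frequencies, which section 8.2.1 measures but the endpoint does not name.
- **A 97.5% chance of a false finding as a plain fact.** That figure needs independence, which repeated visits on related cytokines are unlikely to satisfy.
- **3.6 false positives whatever the truth.** The count applies only if the arms differ on no marker. Any true difference lowers it.
- **Markers will be chosen after looking at this trial's data.** Section 8.2.1 says only that others might be measured. It does not say whose preliminary findings are meant, or whether they would be seen by arm.

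It is also fair that a separate test for each marker at each visit is the natural reading of section 10.2.2 and is not spelled out. The same lack of adjustment applies to the MSFC, EDSS and MRI endpoints, which are not counted here.

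**Conclusion.** The point holds as a minor improvement to the analysis plan. The immune endpoint implies 72 uncontrolled comparisons, with 3.6 false positives expected at 5% per test (1.8 at 2.5%, 7.2 at 10%). This rests on three assumptions: the arms differ on no marker, the stated level applies to each test, and each marker is tested at each visit. The probability of at least one is 97.5% under independence and lower otherwise. The open marker list could raise the count, but the documents do not show that it will, or that additions would follow from unblinded trial data. The primary analysis is not affected. The planned correlation of immune changes with clinical outcome would add tests not counted here, and section 10.2.2 gives no method for it.

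**What to change.** In section 10.2.2:

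1. For each of the 18 endpoint markers, fit one repeated-measures model to months 3, 6, 9 and 12, with baseline as a covariate and the marker transformed if skewed.
2. Pre-specify one treatment contrast per marker, for example the average difference over months 3 to 12. This gives 18 tests and 0.9 expected false positives at 5%.
3. Report the difference at each visit with a confidence interval from the same model.
4. Show Benjamini-Hochberg adjusted values across the 18 markers beside the nominal p-values.
5. Report the tetanus-toxoid frequencies and any later-added markers separately as exploratory, and state in section 8.2.1 where the preliminary findings would come from.

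No visit, sample or assay changes. The cost is a little more analysis work and fewer nominally significant markers. A single averaged contrast may dilute an effect that changes over time. That is a real possibility here, since ECP frequency falls over the year (section 6.2), and it is the reason for keeping the per-visit estimates.
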